9.14 Laboratory Analyses

Blood samples will be drawn from the participants at screening (Visit 1, Day 0), baseline (Visit 2, Day 1), V3, V4, V5, V6, V7, V8, and at the End of Study visit (V9) as indicated in the schedule of assessments.

Protection of subject confidentiality will extend to all data generated from the assaying of these samples. These samples will be alphanumerically coded and the persons performing the analysis will not be aware of the subject's identity or the product they received.

At screening (Visit 1), 8 hour fasting:

- 1. Two EDTA vacutainer tubes to generate whole blood for:
 - a. CBC analysis
 - b. Hb-A1c analysis
- 2. One SST vacutainer tube to generate serum for:
 - a. electrolytes (Na, K, Cl), fasting glucose, eGFR, creatinine, AST, ALT, and total bilirubin analysis

At baseline (Visit 2)

- 1. One BD vacutainer tube to generate whole blood for:
 - a. NAD+
- 2. Two SST vacutainer tubes to generate Pre-Prandial serum for:
 - a. Fasting Glucose analysis
 - b. Fasting Insulin analysis
- 3. One BD vacutainer tube to generate whole blood for:
 - a. ATP/AMP analysis
 - b. GSH/GSSG analysis
- 4. Twelve SST vacutainer tubes to generate serum for:

- a. Fasting Glucose analysis (one per time point tube)
- b. Fasting Insulin analysis (one per time point tube)

Visit 3:

- 1. One BD vacutainer tubes to generate whole blood for:
 - a. NAD+

Visit 4:

- 1. One BD vacutainer tubes to generate whole blood for:
 - a. NAD+

Visit 5

- 1. One BD vacutainer tube to generate whole blood for:
 - a. NAD+
- 2. Two SST vacutainer tubes to generate Pre-Prandial serum for:
 - a. electrolytes (Na, K, Cl), eGFR, creatinine, AST, ALT, and total bilirubin, fasting Glucose and Fasting Insulin analysis
- 3. One BD vacutainer tube to generate whole blood for:
 - a. ATP/AMP analysis
 - b. GSH/GSSG analysis
- 4. Twelve SST vacutainer tube to generate Post-Prandial serum for:
 - a. Fasting Glucose analysis (one per time point tube)
 - b. Fasting Insulin analysis (one per time point tube)
- 5. One EDTA vacutainer tubes to generate whole for:
 - a. CBC analysis

Visit 6

- 1. One BD vacutainer tube to generate whole blood for:
 - a. NAD+
- 1. Two SST vacutainer tubes to generate Pre-Prandial serum for:
 - a. electrolytes (Na, K, Cl), eGFR, creatinine, AST, ALT, and total bilirubin, fasting Glucose and Fasting Insulin
- 2. Twelve SST vacutainer tube to generate Post-meal serum for:
 - a. Fasting Glucose analysis (one per time point tube)
 - b. Fasting Insulin analysis (one per time point tube)
- 3. One BD vacutainer tube to generate whole blood for:
 - a. ATP/AMP analysis
 - b. GSH/GSSG analysis

- 4. One EDTA vacutainer tubes to generate whole blood for:
 - a. CBC analysis

Visit 7

- 1. One BD vacutainer tube to generate whole blood for:
 - a. NAD+

Visit 8

- 1. One BD vacutainer tube to generate whole blood for:
 - a. NAD+

At the end of the study (Visit 9)

- 1. One BD vacutainer tube to generate whole blood for:
 - a. NAD+
- 2. Two SST vacutainer tube to generate Pre-Prandial serum for:
 - a. electrolytes (Na, K, Cl), eGFR, creatinine, AST, ALT, and total bilirubin, fasting Glucose and Fasting Insulin analysis
- 3. One BD vacutainer tube to generate whole blood for:
 - a. ATP/AMP analysis
 - b. GSH/GSSG analysis
- 4. Twelve 8.5mL SST vacutainer tube to generate Post-Prandial serum for:
 - a. Fasting Glucose analysis (one per time point tube)
 - b. Fasting Insulin analysis (one per time point tube)
- 5. One EDTA vacutainer tubes to generate whole blood for:
 - a. CBC analysis

The total blood volume collection for the laboratory assessments listed above will be approximately 250 mL, over the period from screening to end of study (approximately 20 days). At any study visit, blood loss per volunteer is not expected to exceed 131.5 mL. Additional blood samples may be collected during the course of the study in order to perform or repeat laboratory tests outlined in the Schedule of Assessments if needed.

HCMC is the central laboratories that will be used in this study to measure blood parameters

University of Washington is the laboratory that will be used for NAD, GHS/GSSG and ATP/AMP analyses in this study.

Urine pregnancy test will be performed at the Prism clinical site.

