9 STUDY ASSESSMENTS

* At the discretion of the Qualified Investigator, any participants falling outside of the screening window (Day -45 to Day -1) due to scheduling issues will be asked to repeat eligibility/screening procedures prior to randomization at baseline.

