9.1 Visit 1 – Screening (Day -45 to Day -14) *

Participants will show up at the clinic in a fasted state (8h) for visit 1. At screening, an informed consent form will be given to the potential volunteer. They will be required to read the information and will be given the opportunity to seek more information if needed, or provided with the option of taking the consent form home to review prior to making their decision. If agreeable, the volunteer will sign the consent form and receive a duplicate of the signed copy. Once consent has been obtained, the screening visit will proceed. Each volunteer will be sequentially assigned a screening number to be entered in the screening and enrollment log.

Screening assessments include:

- 1. Review medical history, concomitant therapies and current health status
- 2. Assess inclusion and exclusion criteria
- 3. Urine pregnancy test for female potential participants that are of child-bearing potential
- 4. Seated resting blood pressure and heart rate measurements
- 5. Weight and height measurements (BMI calculation)
- 6. Physical exam
- 7. EKG
- 8. Collect fasted blood samples for the analysis of Complete Blood Count (CBC), HbA1c, electrolytes (Na, K, Cl), fasting glucose, eGFR, creatinine, AST, ALT, and total bilirubin
- 9. Complete maximum heart rate treadmill test (Section 9.12.6)
- 10. Dispense 3-Day Food Record and sleep diary
- 11. Dispense salivary collection kit and instruct participants on use (Section 9.12.5)

The next visit will be scheduled for potentially eligible participants for baseline (Day 1).

Reminders for participants prior to their next in-clinic visit:

- 1. Abide by instructions for medications as per Section 7.3.1 and OTC medications, supplements, and food/drinks as per Section 7.3.2
- 2. Complete and return the Food record for the three days prior to baseline visit for review
- 3. Maintain current level of physical activity and maintain and record sleep schedule in diary
- 4. Participants will be advised follow the dietary guidelines (see appendix 15.3)
- 5. Participants will collect baseline salivary cortisol the morning of their Baseline Visit (Section 9.12.5)

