9.2 Run-in period – 2 weeks (Day -13 to Day 0)

Participants will undergo a 14 days run-in period.

Participants are reminded to follow the dietary guidelines 15.3, avoid the consumption of the medications and supplements as per 7.3.1 and 7.3.2, collect saliva the morning of the next in-clinic visit, maintain current level of physical activity and maintain and record sleep schedule.

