9.7 Washout period (Day 9 to Day 15+3 Days)

Participants will undergo a 7-day washout prior to visit 6.

Participants are reminded to follow the dietary guidelines 15.3, avoid the consumption of the medications and supplements as per 7.3.1 and 7.3.2, collect saliva the morning of the next in-clinic visit, and maintain current level of physical activity and maintain and record sleep schedule.

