9.11 Visit 9 – End of the Study (period 2- Day 8+1 Day)

Participants will return to the clinic fasted (8h) for Visit 9 assessments with unused investigational product, completed Subject sleep and treatment diary, saliva kit, and food records.

Visit 9 assessments include:

- 1. Review concomitant therapies
- 2. Seated resting blood pressure and heart rate measurements
- 3. Weight measurements (BMI calculation)
- 4. Return unused investigational product in the original packaging and remnants and calculate compliance by counting the returned unused investigational product
- 5. Physical Exam
- 6. Collect Food Record and Subject sleep and treatment diary for review
- 7. Return saliva collection kit
- 8. Review AEs
- 9. Collect blood sample at T=0 (pre-meal) for fasting serum glucose, insulin, Complete Blood Count (CBC), electrolytes (Na, K, Cl), eGFR, creatinine, AST, ALT, total bilirubin
- 10. Administer the investigational product
- 11. Standardized meal provided (see appendix 15.2)
- 12. Collect post-meal blood sample for serum glucose and insulin analysis at:
 - a. T=15min
 - b. T= 30min
 - c. T=45min
 - d. T=60min
 - e. T=90min
 - f. T=2hrs
- 13. Collect blood sample at T=2 hours (post-meal) for NAD+
- 14. (Optional) Measure NADH with skin fluorescence
- 15. Complete treadmill exercise protocol (Section 9.12.7)
- 16. (Optional) Measure NADH with skin fluorescence
- 17. Collect blood sample for GSH/GSSG and ATP/AMP Analyses
- 18. Administer CIS questionnaire

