9.12.7 Treadmill Exercise

Participants will determine their max heart rate (HR) in the clinic at visit 1 (screening, Day 0) via graded treadmill test with a chest strap heart rate monitor (Section 9.12.6). Eligible participants will return and exercise on the treadmill at visit 2 (period 1, Day 1), visit 5 (period 1, Day 8), visit 6 (period 2, Day 1), and visit 9 (period 2, Day 8). On the day of the exercise, participants will be instructed to warm up on the treadmill first for five minutes at a leisurely walking pace. When the participants are ready, speed will be increased to 60% of participant's HRmax with 5% grade incline and they will be instructed to walk on the treadmill for 30 minutes or until exhaustion (11).

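### Do the 20 days and 250 mL in Protocol 9.14, which sit badly with the visit calendar and tube list, call for a change to the plan?

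*Protocol*

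**What the plan says.** The closing paragraph of Protocol 9.14 gives total blood collection as "approximately 250 mL, over the period from screening to end of study (approximately 20 days". It adds that no single visit is expected to take more than 131.5 mL.

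The calendar is set out elsewhere in section 9:

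- 9.1 is headed "Screening (Day -45 to Day -14".
- 9.2 is headed "2 weeks (Day -13 to Day 0" and says "Participants will undergo a 14 days run-in period".
- 9.7 is headed "Washout period (Day 9 to Day 15+3 Days".
- 9.11 is headed "End of the Study (period 2- Day 8+1 Day".

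Two other labels for screening do not match 9.1. The note at the start of section 9 refers to participants "falling outside of the screening window (Day -45 to Day -1". Section 9.12.7 has "visit 1 (screening, Day 0", and 9.14 uses the same Day 0 label.

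Section 9.14 lists tubes visit by visit. It prints a size only for the twelve post-meal serum tubes at Visit 9 (8.5 mL). Section 9.12.3 says tubes are filled according to a chart that the protocol does not reproduce.

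**The concern.** The stated duration is about half the shortest interval that 9.1 to 9.11 allow. The two alternative screening labels leave no room for the two-week run-in.

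The volume also looks small. Visits 2, 5, 6 and 9 are near-identical meal-test visits, each with twelve post-meal glucose and insulin tubes. If the 8.5 mL printed for Visit 9 applied to all four, the total would be about twice what is stated.

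This is the protocol's only statement of total blood burden on healthy volunteers, and the protocol goes to the IRB (13.1). If it were materially wrong, the ethics committee would have a poor description of what participants undergo. The consent pages are not available, so it cannot be seen whether participants were given the same figures.

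**Working it through.** **Duration.** The inputs are the day labels in 9.1, 9.2, 9.6, 9.7 and 9.11. The run-in from Day -13 to Day 0 is 14 days only if Day 0 is counted, so Day 0 exists.

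- Period 1 ends on Day 8 and washout is Days 9 to 15, so Period 2 Day 1 is study Day 16.
- Visit 9 is Period 2 Day 8: 16 + 7 = study Day 23. All windows are plus-only, so this is the earliest date.

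The attempt to reproduce about 20 days uses elapsed days = 23 − starting day:

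| Starting point | Elapsed days |
|---|---|
| Visit 2, Day 1 | 23 − 1 = 22 |
| Screening as Day 0 (9.12.7, 9.14) | 23 − 0 = 23 |
| Screening as Day -1 (section 9 note) | 23 − (−1) = 24 |
| Screening at Day -14 (9.1, latest) | 23 − (−14) = 37 |
| Screening at Day -45 (9.1, earliest) | 23 − (−45) = 68 |

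The +3 days on washout raise the upper end to 71. If the +1 day windows at Visits 2, 5 and 6 or 9 also accumulate, it can reach 74. Section 9.14 roughly agrees with its own Day 0 label, but not with 9.1 and 9.2.

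**Volume.** The tube counts come from 9.14:

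| Type | Count |
|---|---|
| SST | 1 (Visit 1) + 4 × 14 (Visits 2, 5, 6, 9) = 57 |
| BD | 4 × 2 (Visits 2, 5, 6, 9) + 4 × 1 (Visits 3, 4, 7, 8) = 12 |
| EDTA | 2 (Visit 1) + 3 × 1 (Visits 5, 6, 9) = 5 |
| Total | 74 |

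What 250 mL implies:

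- Averaged over all tubes: 250 / 74 = 3.38 mL each.
- With the printed size honoured and those tubes full: 12 × 8.5 = 102 mL, leaving (250 − 102) / 62 = 2.39 mL for each of the others.

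Two scenarios follow. The 2 and 3.5 mL values are assumptions.

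- *8.5 mL only where printed:* 102 + 62 × 2 = 226 mL, or 102 + 62 × 3.5 = 319 mL.
- *Every SST tube a full 8.5 mL:* 57 × 8.5 = 484.5 mL. The other 17 tubes at 2 mL bring this to 518.5 mL. At 4.17 mL they bring it to 555.3 mL, where 4.17 = (131.5 − 14 × 8.5) / 3 is the room left under the per-visit ceiling at a 17-tube visit.

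The first scenario contains 250 mL. The second is 2.1 to 2.2 times 250 mL, but it carries a size over to 45 SST tubes that have none printed and assumes full draws.

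**Where the figures are used.** Neither number appears in the eligibility criteria, withdrawal rules, compliance rule, safety reporting, sample-size section or analysis section of the protocol, and neither appears in the SAP. The SAP's efficacy comparisons run from Day 1 to later visits within each period, so the day label given to screening does not enter them.

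**The case for a change.** The case for acting is that the duration is contradicted outright, with no assumption needed, and that the volume is probably understated. Two visits at the per-visit figure would already exceed the total (2 × 131.5 = 263 mL), and that figure fits a 17-tube visit using 8.5 mL serum tubes. Venipuncture is the only risk named in 13.3, so the blood total deserves to be right, and correcting it costs little.

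The duration point stands in full. On volume, it stands that 250 mL cannot be verified and that a higher total is plausible, given four similar visits.

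The stronger volume claim does not stand. The 131.5 mL figure is an upper bound, and an upper bound cannot conflict with a smaller total unless a visit is shown to come near it. Tube size is not draw volume when filling follows a chart. The documents set no limit on total volume that a larger figure would breach. With enrolment complete according to SAP 1.8, a revised sentence would not alter what any participant was asked to do.

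**Conclusion.** No change to the plan follows. The stated duration is short by 17 days at least (37 − 20) and 48 at most (68 − 20) before windows, taking 9.1, 9.2, 9.7 and 9.11 at face value. That is a clerical slip linked to three inconsistent screening-day labels, and the passages should be reconciled whenever the text is next reissued. The volume is not shown to be wrong. It lies inside the 226 to 319 mL range if 8.5 mL applies only where printed, and below the 519 to 555 mL range if every serum tube is a full 8.5 mL. The protocol does not say which holds, and the laboratory's tube and fill chart would settle it.

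Both figures are descriptive. Correcting them would improve the IRB record but would leave eligibility, conduct, endpoints, power and every analysis as they are. This conclusion rests on the documents as available, without the consent text.

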9.15 Termination of the Trial

In the case of premature termination of the trial, participating investigators/participants, and the Institutional Review Board must be promptly informed of the termination.

9.16 Protocol Amendments

If amendments to the study protocol are required after approval such changes will be captured in writing the reasons for the change documented and signed and dated by the sponsor. Any such amendments may be subject to IRB review/approval prior to implementation. Exception: if it becomes necessary to alter the protocol to eliminate an immediate hazard to participants, an amendment may be implemented prior to IRB approval. In this circumstance, the Investigator must notify IRB in writing within five (5) working days of the implementation.

investigate the safety and efficacy of RiaGev[™] in healthy adults

10 SAFETY INSTRUCTIONS AND GUIDANCE

10.1 Adverse Events and Laboratory Abnormalities

10.1.1 Adverse Events

An adverse event (AE) is any untoward medical occurrence in a clinical investigation participant who has been administered an investigational product and does not necessarily have a causal relationship with this treatment. An AE can be any unfavorable and unintended sign (including an abnormal laboratory finding), symptom, or disease temporally associated with the use of a product, whether or not it is considered related to that product. Pre-existing conditions that worsen during a study are to be reported as AEs.

During the study, participants should record any adverse effects in their diary. At each visit the participant will be asked, "Have you experienced any difficulties or problems since I saw you last?". Any adverse events (AEs) will be documented in the study record and will be classified according to the description, duration, intensity, frequency, and outcome. The qualified investigator will assess any AEs and decide causality.

Intensity of AEs will be graded on a three-point scale (mild, moderate, severe) and reported in detail in the study record.

Mild: Awareness of event but easily tolerated

Moderate: Discomfort enough to cause some interference with usual activity

Severe: Inability to carry out usual activity

The causality relationship of investigational product to the adverse event will be assessed by the qualified investigator as either:

Most probable: There is a reasonable relationship between the investigational product and AEs.

The event responds to withdrawal of investigational product (dechallenge) and

recurs with rechallenge when clinically feasible.

Probable: There is a reasonable relationship between the investigational product and AEs.

The event responds to dechallenge.

Possible: There is a reasonable relationship between the investigational product and AEs.

Dechallenge information is lacking or unclear.

Unlikely: There is a temporal relationship to the investigational product administration but

there is no reasonable causal relationship between the investigational product and

the AEs.

Not related: There is no temporal relationship to investigational product administration or

there is a reasonable causal relationship between non-investigational product,

concurrent disease or circumstance and the AEs.

10.1.2 Serious Adverse Event

A serious adverse event (SAE) is any experience that suggests a significant hazard, contraindication, side effect or precaution. It is any AE that results in any of the following outcomes:

- 1. Death
- 2. A life-threatening adverse event
- 3. Inpatient hospitalization or prolongation of existing hospitalization
- 4. A persistent or significant disability or incapacity
- 5. A congenital anomaly/birth defect in the offspring of a participant who received the study treatment

Important medical events that may not be immediately life-threatening or result in death or hospitalization but may jeopardize the participant or may require intervention to prevent one of the outcomes listed above. Examples of such events are intensive treatment in an emergency room or at home for allergic bronchospasm; blood dyscrasias or convulsions that do not result in hospitalization; or the development of drug dependency or drug abuse.

10.1.3 Unexpected Adverse Reaction

An unexpected adverse reaction is an adverse reaction, the nature and severity of which is not consistent with the applicable product information (e.g., Investigator's Brochure for an unapproved investigational product or package insert/summary of product characteristics for an approved product).

10.1.4 Laboratory Test Abnormalities

The investigator must assess the clinical significance of all abnormal laboratory values as defined by the compendium of normal values for the reference laboratory.

Any treatment emergent abnormal laboratory result which is clinically significant, i.e., meeting one or more of the following conditions, should be recorded as a single diagnosis on the AEs form in the study record:

- 1. Accompanied by clinical symptoms
- 2. Leading to interruption or discontinuation of the investigational product
- 3. Requiring a change in concomitant therapy

This applies to any protocol and non-protocol specified laboratory result from tests performed after the first dose of the investigational product, which falls outside the laboratory reference range and meets the clinical significance criteria for liver and kidney tests as well as for hematology and clinical chemistry, etc. (i.e. AST and/or ALT \geq 2 x ULN).

This does not apply to any abnormal laboratory result which falls outside the laboratory reference range but which does not meet the clinical significance criteria or those which are a result of an AE which has already been reported.

Any laboratory result abnormality fulfilling the criteria for a serious adverse event (SAE) should be reported as such, in addition to being reported as an AE in the study record.

10.2 Treatment and Follow-Up Of AEs And Laboratory Abnormalities

10.2.1 Treatment and Follow-up of AEs

AEs, especially those for which the relationship to the investigational product is suspected, should be followed up until they have returned to baseline status or stabilized.

If after follow-up, return to baseline status or stabilization cannot be established, an explanation should be recorded in the study record.

10.2.2 Treatment and Follow-up of Laboratory Abnormalities

In the event of participant-initiated withdrawal or clinically significant unexplained abnormal laboratory test values, the participant will be withdrawn from the treatment and will remain in the study and be required to attend all remaining study visits as part of a safety arm.

10.3 Reporting of SAEs And Unexpected Adverse Reactions

The qualified investigator will be responsible for classification of an AE as an SAE within 24 hours of notification. Causality should be signed off by the qualified investigator prior to reporting to ethics and regulatory bodies. Notification of any serious adverse events must be made in writing to the study sponsor. The IRB will be notified of all product related SAEs and unexpected adverse reactions.

11 STATISTICAL EVALUATION

11.1 Determination of Sample Size

The planned total sample size will be 18 with 9 participants randomized to each treatment schedule. This sample size will enable detection of a difference of 8.7 pMol/mg protein in NAD+ concentration between the two treatments at an overall 5% significance level and 80% power. This sample size takes into account a loss to follow up rate of 20%.

This calculation is based on a critical difference in NAD+ concentration, between NR and placebo of 6.1 pMol/mg protein and a standard deviation of 11.04 units reported in a study by Martens et al. (2018)(13).

11.2 Analysis Plan

The **Safety Population** will consist of all participants who received any amount of either product, and on whom any post-randomization safety information is available.

The **Intent-to-Treat (ITT) Population** consists of all participants who received either product and on whom any post-randomization efficacy information is available.

The **Per Protocol (PP) Population** consists of all participants who consumed at least 80% of treatment or placebo doses, do not have any major protocol violations and complete all study visits and procedures connected with measurement of the primary variable.

